4.1. Sample Size

On the basis of previous post-hoc analyses of pain (Cattaneo et al 2017) and of similar studies ([Folstein et al, 1975](#)), assuming a standard deviation of 2 it is anticipated that a sample size of 144 subjects would permit detection of a 1 point treatment difference in the NRS between safinamide and placebo at the 5% significance level with 80% power. A 1-point treatment difference is considered to be a clinically meaningful treatment effect ([Rascol et al, 2016](#)).

Approximately 220 subjects will be screened to achieve approximately 177 randomly assigned to study treatment and of which approximately 144 subjects completing the study (n= 96 and n= 48 evaluable subjects in the active and placebo group respectively).

Since March 2020, the COVID-19 emergency has impacted the feasibility of the trial, which is being conducted in a vulnerable group of patients. Upon receipt of the guidance “Statistical Considerations for Clinical Trials During the COVID-19 Public Health Emergency” issued by FDA on June 2020, released with the aim of helping sponsors ensure that trials conducted during the Covid-19 emergency could continue, where appropriate, to provide interpretable findings with correct statistical quantification of uncertainty, the Sponsor performed a Blind Data Review Analysis of the primary endpoint data (pain severity) for the 26 patients who had completed the study as of June 2020.

The results of the analysis show that the standard deviation used in the original sample size estimation (SD = 2) was a conservative overestimate of the observed SD from the actual trial data, which was 1.43 at the time of the blinded data review.

Based on this, the Standard Deviation, for the estimation of sample size has now been amended to 1.50, and the power has been maintained as 80%. New sample size estimates have been performed considering different magnitudes of Treatment Difference but keeping

the same assumptions of screen failure rates and dropout rates. These are summarized below in [Table 4.1](#).

Table 4.1 Sample Size Estimations

SCENARIO	SAMPLE SIZE
Power = 80% Standard deviation = 1.5 Treatment Difference = 1 point	Pts to screen= 132 Pts to randomize= 105 Pts completing study= 84
Power = 80% Standard deviation = 1.5 Treatment Difference = 1.5 points	Pts to screen= 66 Pts to randomize= 51 Pts completing study= 39
Power = 80% Standard deviation = 1.5 Treatment Difference = 2 points	Pts to screen= 39 Pts to randomize= 30 Pts completing study= 24

Currently, it is planned to keep the initial conservative estimate of treatment difference as 1 and change the SD to 1.5 in line with what was observed with the Blind Data Review Analysis. Using these parameters, up to 132 participants will be screened to achieve up to 105 randomized, to have approximately 84 patients complete the study (56 in the active and 28 in the placebo group respectively).

However, given the continuous and uncertain impact that COVID-19 outbreak is having in the countries participating in the trial, any of other scenarios might be adopted if at the end of December 2020, the above enrollment goal will not be achieved. From the table above it can be seen that if the treatment difference is greater than 1, statistical significance can be achieved with a substantially lower sample size. Thus, the study maintains its robustness.

4.2. Randomisation, Stratification, and Blinding

Subjects will be randomised to double-blinded treatment in a 2:1 ratio to receive either safinamide or placebo at Visit 2 (day 1). An interactive web response system (IWRS) will be used for the randomisation. PPD Biostatistics will generate the randomisation schedule for IWRS, which links sequential subject randomisation numbers to treatment codes.

In case of an emergency, the investigator has the sole responsibility for determining if unblinding of a subject's treatment assignment is warranted and should make every effort to contact the sponsor prior to unblinding a subject's treatment assignment unless this could delay emergency treatment of the subject. If a subject's treatment assignment is unblinded,

the sponsor must be notified within 24 hours after breaking the blind. The date and reason that the blind was broken must be recorded in the source documentation and case report form, as applicable.

4.3. Analysis Set

The analysis sets that will be used in this study are detailed below in [Table 4.2](#). Membership to each analysis set will be reviewed and confirmed prior to database lock.

The number and percentage of subjects in each analysis population will be summarised by the treatment they were randomised to as well as for the total number of subjects. A listing will also be produced displaying subjects excluded from each population.

Table 4.2 Analysis Populations Definition

Population	Description
Full analysis set	The FAS is defined as all randomized subjects in the study, with at least one measurement of the primary efficacy variable following at least one dose of study medication. Summaries on the FAS will be performed for all efficacy endpoints. Subjects in this analysis set will be summarized according to the treatment they were randomly assigned to.
Per Protocol	The PP Set will be a subset of subjects in the FAS who completed the study and for whom no relevant protocol deviations were documented. Identification of relevant protocol deviations will occur on a blinded review meeting preceding database lock. A second analysis of the primary efficacy endpoint will be based on the PP Set. All subjects in the PP Set will be summarized according to the treatment they were assigned to.
Safety	The Safety Set will include all randomized subjects assigned to study intervention and who take at least 1 dose of study medication. The Safety Set will be used for the analysis of all safety endpoints. All subjects in the Safety Set will be summarized according to the treatment they actually received (according to the Drug Accountability eCRF page).

The Screened Population will include all subjects who sign the informed consent form (ICF). This population will be listed but not used for statistical analyses. The data from this population will be summarized and used for presenting subject study disposition

All Enrolled population includes all subjects who signed the informed consent form (ICF) and enrolled into the study. The data from this population will be summarized and used for presenting subject study disposition.

The decision whether a protocol deviation is relevant or not for the exclusion of subjects from the per protocol (PP) set will be made case-by-case in a blind data review meeting.

The primary analysis of the primary efficacy variable will be based on the FAS data set. A secondary analysis of the primary efficacy parameter will be based on the PP set.

All other secondary efficacy analyses will be based on the FAS.

Safety analyses will be based on the safety analysis (SA) set.

5. Visit Attendance

The number and percentage of subjects who attended a visit or received a safety call will be presented for the following visits:

- Visit 2 (Baseline or Day 1)
- Visit 3 (Day 28)
- Visit 4 (Day 56)
- Visit 5 (EoT or Day 112)
- Follow-up Call

For Subjects with on-going site visits, wherever possible all efforts will be made to have the patient attend the hospital for their on-site study visits accordingly to schedule in the protocol. Assessment will be performed via phone call for Adverse event, Concomitant medication and e-questionnaires MDS-UPDRS, CGI-s and CGI-c if site visit is not possible. Anticipated data which will be missing due to COVID-19 outbreak is mostly LAB and ECG which requires on-site attendance.

6. Subject Disposition

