3.1. Overall Study Design and Plan

This is a Phase IV, international, multicentre, randomised, double-blind, placebo-controlled study in IPD male and female subjects 30 years of age or older, experiencing motor fluctuations and PD related chronic pain while on stable doses of L-Dopa. The duration of the study for each subject is 19 weeks (including the Screening period). Subjects will be randomised to receive either active or placebo in a 2:1 ratio, respectively. A telephone follow-up call will be performed 1 week after the end of treatment.

[figure not shown]
Study consists of two periods, screening (1-2 weeks) and a treatment period (16 weeks), with a follow-up call at 1 week after treatment, so total duration of 19 weeks.

The Screening visit (Visit 1) should occur up to 14 days before Day 1. At baseline (Visit 2, Day 1), eligible subjects will enter the treatment period and will receive study medication 50 mg (from Day 1 to Day 7) and then 100 mg (from Day 8 onwards), to be taken orally once daily (od). Following completion of all baseline assessments, they will receive the first dose of study medication at the study centre. Thereafter, study drug will be taken, at home, each morning along with their first morning dose of L-Dopa and other (if any) PD medications. On Day 8 the dose of study drug will be increased, at home, to 100 mg od. Each subject will receive treatment for 16 weeks, with visits at Week 0/Day 1 (baseline) and at Weeks 4, 8 and 16 (or early termination).

From day 1 onwards, participant will record the use of PRN medications along with indicating the worst pain experienced on a daily basis.

Diagram of Study Schedule:

Figure 1: Diagram of Study Schedule

Randomisation is in a 2:1 ratio of active:placebo; up to 132 participants will be screened to achieve up to 105 randomized, to have approximately 84 patients complete the study (56 in the active and 28 in the placebo group respectively). The detailed description is present in [Section 4.1](#).

Subjects will take their allocated study drug in accordance with the assigned regimen:

Safinamide: 50 mg (from Day 1 to Day 7) and then 100 mg (from Day 8 onwards)
or
Placebo: 50 mg (from Day 1 to Day 7) and then 100 mg (from Day 8 onwards)

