10.1. Primary Efficacy Endpoint

Pain severity data will be derived from the daily diary.

The primary endpoint evaluated in this study is the mean change in pain severity (“average worst pain experienced in the last 7 days”, i.e. average of the worst pain score on each of the 7 days preceding the site visit), as assessed by an 11-point NRS, from baseline to Week 16. For efficacy analysis, at least 4 out of 7 daily pain scores are needed to calculate a valid average over 7 days.

The null hypothesis for the primary endpoint is that safinamide is no better than placebo in managing pain; thus $\mu(\text{Safinamide}) > \mu(\text{Placebo})$, where μ represents the population mean change in pain severity score from baseline at Week 16 and a negative change would indicate improvement.

The primary efficacy endpoint, change from baseline to Week 16 in pain severity score, will be analysed using a mixed model repeated measures (MMRM) using visit on subject ID as

the repeated factor with unstructured covariance term (REPEATED VISIT/SUBJECT=SUBJID TYPE=UN). If convergence is not achieved, then other covariance structures will be investigated such as compound symmetric (TYPE=CS). The model will include fixed effects terms for treatment, country, visit and regular pain medication use at baseline (yes or no) and covariate term for pain severity score at baseline. The method above (e.g. MMRM) is unbiased under the MAR assumption and can be thought of as aiming to estimate the treatment effect assuming that after withdrawal, subjects would have continued on a similar trajectory to their peers in the same arm who have the same covariates.

The likelihood-based mixed-effect model repeated measure will be performed using a SAS PROC MIXED procedure, and the Kenward-Roger method for degrees of freedom will be applied. The restricted maximum likelihood (REML) method will be used for estimation. The least square (LS) means of change from baseline in pain severity along with the associated SE and 95% CIs will be calculated from the model at each time point. The LS mean difference between the treatment groups at Week 16 will also be reported, along with the corresponding SE, 95% CIs, and the p-value derived for the difference between treatment arms (safinamide – placebo). No adjustment is being made for multiple comparisons.

Results for time points other than Week 16 (Weeks 4 and 8) will be presented in both the above discussed model-adjusted and descriptive forms.

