10.3. Secondary Efficacy Endpoints

The PGI-C, CGI-C, CGI-S, and MDS-UPDRS will be analysed at weeks 4, 8 and 16 using the same statistical methods i.e. MMRM as for the primary efficacy parameter defined in [Section 10.1](#) by replacing covariate of pain severity at baseline with respective efficacy parameter

Pain severity score at Weeks 4 and 8 will also be analysed by the same MMRM method used for Pain severity score at Week 16 as defined in [Section 10.1](#)

Change from baseline in HADS at Week 16 will be analysed using an ANCOVA. The model will include treatment, baseline HADS and country as fixed effects. The Least Square (LS) means of the change from baseline in HADS score along with the associated SE and 95% CIs will be calculated, and the p-value derived for the difference between treatment groups at Week 16 will be presented.

Percentage of pain responders defined as subjects with reduction in pain severity of ≥ 2 points (“average worst pain experienced in the last 7 days”) as assessed by an 11-point NRS, compared to baseline), will be analysed at weeks 4, 8 and 16 using a Cochran-Mantel-Haenszel adjusted test of the difference in proportions between the two treatment groups. Country will be used as the stratification factor. A 95% confidence interval of the difference in proportions and p-value will be reported. For percentage of pain responders, a missing value at each visit will be imputed to indicate that a subject was a non-responder i.e. a Worst-Case imputation. It will be summarized for both Observed data and Imputed data.

The analysis of amount of concomitant PRN PD pain medications (as reported in the Patient Diary) and concomitant pain drugs (as reported on the ‘Concomitant Medications’ eCRF page) will be summarized in two ways i.e. the number of days on which pain medication was taken in the 7 days preceding Visits at Weeks 4, 8 and 16 and the number of patients taking pain medication in the 7 days preceding Visits at Weeks 4, 8 and 16.

The number of days that pain medication was taken will be analysed using a two-sided Mann Whitney test at the 5% level of significance level to test the null hypothesis of no difference between the two treatments. In case if the patient has not taken any pain medication in the 7

days preceding Visits at Weeks 4, 8 and 16, then the number of days will be considered as zero for that particular patient for that particular visit.

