14.1. Schedule of Activities (SoA)

Visit	1 Screening	2 Baseline	3 Interim Week 4	4 Interim Week 8	5 EoT Week 16	6 Call	
Day / Procedure	(up to 14 days before Day 1)	1	28 ± 3	56 ± 3	112 ± 3	119 ± 3	Notes
Informed consent	X						After informed consent signing, enter details in IWRS to obtain screening number.
Eligibility criteria	X	X					Check prior to randomisation/ 1 st dose of study medication
Randomisation		X					Use IWRS to randomise
Demographics	X						Age, sex, race, smoking and alcohol use
Medical history	X						PD diagnosis, Hoehn & Yahr staging, etc.
Vital signs	X	X			X		Heart rate, systolic and diastolic blood pressure

Visit	1 Screening	2 Baseline	3 Interim Week 4	4 Interim Week 8	5 EoT Week 16	6 Call	
Day / Procedure	(up to 14 days before Day 1)	1	28 ± 3	56 ± 3	112 ± 3	119 ± 3	Notes
Physical examination and neurological examination	X				X		
MMSE	X						
eDiary Issue, Training and return	X	X			X		
eDiary Review		X	X	X	X		Participant to complete diary for 7 days prior to each visit.
NRS Review		X					For eligibility: PI checks NRS score to confirm eligibility
MDS-UPDRS		X	X	X	X		
CGI-S		X	X	X	X		
CGI-C			X	X	X		
PGI-C			X	X	X		
HADS		X			X		

Visit	1 Screening	2 Baseline	3 Interim Week 4	4 Interim Week 8	5 EoT Week 16	6 Call	
Day / Procedure	(up to 14 days before Day 1)	1	28 ± 3	56 ± 3	112 ± 3	119 ± 3	Notes
Blood draw	X				X		For Haematology & Clinical chemistry
Pregnancy test		X			X		Urine dipstick test for WOCBP only
Prior and concomitant medications	X	X	X	X	X	X	
Adverse events	X	X	X	X	X	X	
Drug Dispense		X	X	X			
Drug accountability			X	X	X		

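### Dosed patients with no usable post-dose pain score fall outside the FAS, so the responder analysis removes them from the denominator and does not count them as non-responders

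*SAP*

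**What the plan says.** FAS entry (SAP 4.3, Table 4.2; same wording in protocol 9.3) is limited to randomised patients "with at least one measurement of the primary efficacy variable following at least one dose of study medication". The primary variable is built from the "average of the worst pain score on each of the 7 days preceding the site visit", and SAP 10.1 adds that "at least 4 out of 7 daily pain scores are needed to calculate a valid average over 7 days".

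SAP 4.3 then makes this the set for the whole of efficacy: "Summaries on the FAS will be performed for all efficacy endpoints", and "All other secondary efficacy analyses will be based on the FAS". No endpoint has its own analysis set, and no responder analysis on all randomised or all dosed patients is planned.

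For responders at Weeks 4, 8 and 16, SAP 10.3 states that "a missing value at each visit will be imputed to indicate that a subject was a non-responder i.e. a Worst-Case imputation". Observed and imputed results are both to be shown.

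On diary timing, the schedule in SAP 14.1 says "Participant to complete diary for 7 days prior to each visit", which puts the first scheduled post-dose window in the week before Week 4. SAP 3.1 reads differently: "From day 1 onwards, participant will record the use of PRN medications along with indicating the worst pain experienced on a daily basis". Protocol Section 8 (Visit 5) requires the end-of-treatment assessments, with diary review, after premature discontinuation. Protocol 8.1.1 lists early termination among the visits for which an NRS average is formed.

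**The concern.** Counting missing as non-response is meant to stop dropouts from improving a responder rate. Here the filter comes first: a patient must already have a post-dose pain measurement before the rule can apply. The patients it misses are those with nothing usable after the first dose, mainly the earliest to leave. Whether a patient is in that group depends on events after randomisation, such as an early adverse event or early withdrawal. If such losses differ between arms, the FAS responder difference is biased.

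Sensitivity analysis (b) in SAP 10.2 has the same gap. It imputes each dropout's worst value from baseline onwards but is run on the FAS. The missed patients should have a baseline score to impute from, because eligibility at randomisation depends on one.

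A smaller consequence concerns endpoints that do not use the diary. CGI-S, CGI-C, PGI-C, HADS and MDS-UPDRS are collected separately, and under the COVID-19 plan (protocol Appendix 10) the rater scales may be taken by phone or on paper. A patient with valid ratings but no valid diary week at any visit would be left out of those analyses too.

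**Working it through.** **1. Planning figures.** Inputs from SAP 4.1: difference 1 point, SD 1.5, 80% power, 5% significance, 2:1 allocation, 84 completers (56:28), 105 randomised. A two-sided t-test with 28 placebo and 56 active patients has power 0.812, and 28 is the smallest placebo group that reaches 80%, so 84 reproduces. With 20% loss, 84 / (1 − 0.20) = 105. Planned non-completers are 105 − 84 = 21, and 105 at 2:1 is 70:35.

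**2. How many could be missed.** The documents give no timing of dropout. On the planning figures the range is 0 to 21.

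**3. Formula.** Let r be the responders in an arm, n the dosed patients, and k those with no usable post-dose NRS, who are all non-responders under the worst-case rule.

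- All dosed: r_A/n_A − r_P/n_P
- FAS: r_A/(n_A − k_A) − r_P/(n_P − k_P)
- Shift = (r_A/n_A) × k_A/(n_A − k_A) − (r_P/n_P) × k_P/(n_P − k_P)

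The shift is positive when the active term is larger and negative when the placebo term is larger, so its sign is not fixed in advance.

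**4. Example.** Assumed: every randomised patient is dosed, with 30/70 and 10/35 responders.

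| No usable post-dose NRS (active, placebo) | Calculation | Difference (points) | Shift (points) |
|---|---|---|---|
| None excluded | 30/70 − 10/35 | 14.3 | – |
| 4, 1 | 30/66 − 10/34 | 16.0 | +1.8 |
| 4, 2 (in proportion to 2:1) | 30/66 − 10/33 | 15.2 | +0.9 |
| 8, 1 | 30/62 − 10/34 | 19.0 | +4.7 |
| 1, 4 | 30/69 − 10/31 | 11.2 | −3.1 |

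**5. Wider range.** Assumed: completer responder rates of 50/30, 40/25 or 60/40%, 21 dropouts, and 25%, 50% or 100% of dropouts with no usable post-dose NRS.

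- Dropouts split 14:7, in proportion to allocation: the FAS overstates the difference by 0.6 to 4.0 points. For example, at 50/30% the all-dosed difference is 28/70 − 8.4/35 = 16.0 points. With half the dropouts excluded, the FAS gives 28/63 − 8.4/31.5 = 17.8.
- Dropouts split 17:4 or 19:2: the overstatement runs up to 14.0 points. That extreme needs 60/40% rates, 19 of 21 dropouts on active, and none of the 21 with a usable score.

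This grid contains no placebo-heavy loss. The last row of the table shows that such loss moves the difference the other way.

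**6. Primary MMRM.** A patient with no post-baseline value adds essentially nothing to the likelihood for change from baseline, so FAS entry costs little there.

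**The case against.** A reader might infer more than the documents support.

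- **That anyone leaving before Week 4 is outside the FAS.** The early-termination assessment in protocol Section 8 and 8.1.1 can supply a usable diary week. If pain is scored daily from Day 1, as SAP 3.1 says, a patient leaving in week 2 or 3 can still qualify. Only patients with nothing usable at any post-dose assessment are lost.
- **That the 4-of-7 rule is part of the FAS definition.** It is stated in SAP 10.1 for calculating an average. Table 4.2 does not say whether a measurement is a valid average or one daily score. The second reading loses fewer patients.
- **That patients with good ratings are generally dropped from the other scales.** One poor diary week does not exclude. Entry requires the ability to keep the diary, site staff review it at visits and retrain as needed, and a caregiver may complete the NRS if the patient is unable to. For HADS, measured after baseline only at Week 16 or early termination, the case is narrower still.
- **That the plan contradicts itself.** Protocol and SAP give the same definition and name the population openly. SAP 10.3 does not promise to cover all randomised patients. This is a design weakness.

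The size can also be challenged. Every count above is assumed, and the 8:1 case needs 9 of the 21 planned non-completers to have no post-dose NRS, almost all on active. The standard error of the 14.3-point difference is √(0.429 × 0.571/70 + 0.286 × 0.714/35), about 9.7 points, so the shifts in the table are well inside sampling error. SAP 4.3 and 6.1 also require FAS counts by arm, a listing of exclusions and discontinuation reasons, so unequal loss would be visible.

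All of this limits the point without removing it. Visible exclusions are still exclusions, a bias smaller than the standard error is still a bias, and a rule labelled worst-case should cover the dosed patients with the least data.

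**Conclusion.** The point holds in limited form. Because FAS entry depends on a post-dose NRS measurement and the FAS governs all secondary efficacy endpoints, dosed patients with no usable post-dose NRS at any assessment leave the responder denominator. Sensitivity analysis (b) misses them as well.

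The number is unknown: 0 to 21 on the planning figures, fewer if early-termination diaries are usable or if a single daily score suffices. With loss in proportion to allocation, the assumed scenarios shift the responder difference by 0.6 to 4.0 points. Unequal loss can move it further, in either direction. The documents do not support saying that the bias favours safinamide.

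The primary MMRM is little affected. The effect on CGI-S, CGI-C, PGI-C, HADS and MDS-UPDRS is minor and confined to a rare patient.

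**What to change.** - Keep the FAS for the primary MMRM.
- Run the responder CMH test at Weeks 4, 8 and 16 on all randomised patients who took at least one dose, grouped by randomised arm, with missing counted as non-response. Stratification by country stays as planned.
- State in SAP 4.3 whether a measurement means a valid 4-of-7 average or a single daily score, and reconcile the two accounts of when pain is scored.
- Minor: for CGI-S, CGI-C, PGI-C, HADS and MDS-UPDRS, require a post-baseline value of that endpoint and not of the NRS.
- Record the change in SAP Section 12, because protocol 9.3 carries the same definition and the same rule for secondary analyses. Make it before unblinding.

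The cost is small. Randomised and dosed patients are already identified for the Safety Set and need only be grouped by randomised arm. No new data are needed and the sample size does not change. The downside is slightly lower responder rates in both arms.
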